4.6 Restrictions

There are no restrictions on diet or exercise for these subjects.

4.7 Treatment Compliance

Administration of all somavaratan doses will be performed in clinic by a trained health care professional during the dose titration period. Subsequent maintenance doses can be administered by trained subjects/caregivers, or a health care professional. Dosing schedules will be established at the time of enrollment. Each dose has a window of ± 2 days, but monthly variability will not affect overall treatment schedule, because dates of administration are relative to the first dose. If a dose cannot be administered within this time window, it will be considered a missed dose, unless the Investigator and Medical Monitor decide to administer the dose as a protocol deviation (e.g., outside of the protocol-specified dosing window of every 15 days ± 2 days). Failure to receive scheduled doses may be cause for withdrawal.

Efforts should be made to complete all protocol specified activities within the allotted time frame. Failure to adhere to the schedule for PK/PD and safety data sample collection may be cause for withdrawal.

4.8 Packaging and Labeling

4.8.1 *Somavaratan*

Somavaratan Drug Product (sterile parenteral study medication, DP) will be provided by the Sponsor to Catalent Pharma Solutions (Catalent). Catalent will label the DP and distribute a sufficient quantity of single-unit dose containers of DP with tamper evident seals to the participating investigational pharmacy at each site. The DP will be provided as labeled 2 mL glass vials with a rubber stopper and a crimp seal with flip top lid or as a disposable autoinjector device (when available). Vials are designed to allow for withdrawal of 1.0 mL (100 mg) of DP. Disposable autoinjector devices are for single use only and provide the ability to select (dial) the prescribed mg dose of somavaratan between 20 and 100 mg (4 separate presentations with 20 mg range each).

4.8.2 *Assembly and Labeling of Somavaratan*

4.8.2.1 Vial and Syringe Configuration

Dispensing of the unit doses into syringes for subject administration for all in clinic dosing events will be the responsibility of the pharmacist or other site healthcare professional in compliance with the site practices and local regulatory requirements.

Dispensing of the unit doses into syringes for subject administration for doses administered outside of the clinic by subject/caregiver will be the responsibility of each subject/caregiver. Dose administration by subject/caregiver will be allowed only after adequate training and documentation of demonstrated understanding by subject/caregiver. Dose administration outside of the clinic will be performed by a health care professional or trained subject/caregiver only.

The DP will be labeled as somavaratan for investigational use only.

4.8.2.2 Somavaratan Autoinjector

Dispensing of the somavaratan autoinjector (when available) to the subject for subject dose administration for all dosing events will be the responsibility of the pharmacist or other site healthcare professional in compliance with the site practices and local regulatory requirements.

Dose administration by subject/caregiver will be allowed only after adequate training and documentation of demonstrated understanding by subject/caregiver. Dose administration outside of the clinic will be performed by a health care professional or trained subject/caregiver only.

The somavaratan autoinjector will be labeled for investigational use only.

4.9 Storage and Accountability

4.9.1 *Somavaratan*

The DP will be stored at 2–8° C at the investigational pharmacy. DP storage at the investigational pharmacy will have restricted access. The DP will be removed from cold storage and allowed to equilibrate to room temperature for a minimum of 30 minutes before subject administration. No special procedures are required for the safe handling of the DP, however, it must be handled gently (e.g., no shaking, agitating, heating under warm water, etc.). The DP will remain stable for a minimum of 8 hours at ambient temperature. Directions for use and administration will be provided. Documentation of somavaratan doses administered will be entered directly by the person administering the doses (subject/caregiver or health care professional) into the interactive web response system (IWRS) provided by Versartis.

4.10 Investigational Product Retention at Study Site

Records will be maintained showing the receipt and disposition of all DP (vials and/or autoinjectors) and other study supplies (if applicable). The Sponsor and/or its designee will routinely monitor and audit the records of DP receipt, supplies, storage, dosage preparation procedures, and records at the investigational pharmacy. For all used DP vials, the empty used vials will be discarded upon satisfactory completion of accountability procedures. All used autoinjectors will be discarded upon satisfactory completion of accountability procedures. Any unused DP will be retained until completion of the study.

Following completion of the clinical phase of the study and Sponsor review of accountability, all unused, used or partially used DP and study supplies will either be returned to the Sponsor (together with the accountability records) or will be destroyed at the clinical site and Certificates of Destruction (or equivalent) provided to the Sponsor.

DP must be controlled and accounted for by the study Investigator or the designee; however, the study Investigator retains primary responsibility for its use and documentation of use. No persons other than those designated as qualified study participants may receive study medication. The study Investigator or physician sub-Investigators are the only persons authorized to provide medication orders or prescribe study treatments.

The study Investigator must ensure that DP is stored under the specified conditions and in a secure location with access limited to those involved in the study or other appropriate study site personnel. Additionally, the study Investigator must allow access to Versartis, Clinical Research Associates (CRAs), auditors and regulatory authorities for inspection of records and investigational product supplies.

5 STUDY PROCEDURES

For subjects who participated in a previous somavaratan study:

- Up to 30 day Enrollment period for Inclusion/Exclusion Criteria; the Day 1 visit may occur simultaneously with the last visit of the subject's previous somavaratan study
- Subjects receiving somavaratan once monthly in a prior Versartis adult GHD study or in this study, irrespective of the cohort assignment and whether they have achieved maintenance dosing, will transition to receive treatment at half of their current dose (rounded down to the nearest even number, minimum dose of 20 mg).
- Monthly dose titration period (Table 2) with adjustments to somavaratan doses as needed
- Twice-monthly treatment with maintenance dose of somavaratan

For new subjects who are either receiving daily rhGH therapy or are treatment naive:

- Up to 30 day Screening period for Inclusion/Exclusion Criteria
 - Minimum of 14 day washout period for subjects currently receiving daily rhGH treatment
- Fixed starting dose (Table 1) with monthly dose titration period (Table 2) with adjustments to somavaratan doses as needed
- Twice-monthly treatment with maintenance dose of somavaratan

All subjects will have Day 8 IGF-I SDS evaluated each month with subsequent dose adjustments made per the Dose Titration Plan (Table 2)

5.1 Screening procedures

Subjects may undergo study specific Screening/Enrollment activities up to 30 days prior to enrollment in the study. Subjects will sign the study-specific informed consent form in the presence of an Investigator prior to any Screening/Enrollment procedures being performed. Subjects are enrolled in the study after fulfilment of the Inclusion/Exclusion Criteria.

5.2 Medical History

A complete medical history and Baseline signs and symptoms will be obtained as part of enrollment activities during the Screening visit.

5.3 Physical Examination

A physical examination will be performed at Screening and quarterly thereafter (Month 3, 6, 9, 12, etc.). During dose titration, a symptom-directed brief physical examination will also be performed at monthly clinic visits. Injection sites will be examined at all clinic visits.

5.4 Vital Signs

Vital signs and weight are measured at the beginning of all clinic visits. Weight will be measured with subject wearing light clothing and without shoes. Pulse rate, respiration rate, body temperature, and systolic/diastolic blood pressure will be measured at all clinic visits with the subject sitting quietly for at least five minutes.

5.5 Clinical Laboratory Tests

5.5.1 Laboratory Parameters

Subjects will be in a seated or supine position during blood collection. Growth hormone stimulation tests (if necessary for diagnosis of GHD) and adrenal stimulation tests will be performed locally according to institutional protocols. Urine tests will be performed locally. All other clinical laboratory tests will be conducted by a central laboratory to be identified by the Sponsor and include the following:

Table 3 List of Laboratory Tests

Hematology:
 
 - Red blood cell (RBC) count - White blood cell (WBC) with differential - Platelet count - Hemoglobin (Hgb) - Hematocrit (Hct) - Mean corpuscular hemoglobin (MCH) - Mean corpuscular hemoglobin concentration (MCHC) - Mean corpuscular volume (MCV) 	
Serum Chemistry:
 
 - Albumin (ALB) - Alkaline phosphatase (ALP) - Alanine aminotransferase (ALT; SGPT) - Aspartate aminotransferase (AST; SGOT) - Blood urea nitrogen (BUN) - Calcium (Ca) - Cortisol (am baseline and stimulated)¹ - Creatinine - Gamma-glutamyl transpeptidase (GGT) - Glucose - Phosphate - Potassium (K) - Sodium (Na) - Total protein - Free T4 - TSH - High-sensitivity C-reactive protein (hs-CRP) 
¹: Adrenal stimulation testing will be performed locally (for subjects without documented history of adrenal insufficiency) at Screening. Additional adrenal testing may be performed at the discretion of the Investigator based on clinical assessment.

Urinalysis: performed locally by Urine Multistix[®] (or similar)
 
 - Bilirubin - Glucose - Ketones - Nitrite - Occult blood - pH - Protein - Urobilinogen 	

Pregnancy test: (for women of child bearing potential)
 
 - Serum at Screening - Urine at all other time points 	

Fasting Lipid profile:
 
 - Total cholesterol - Low density lipoprotein (LDL) - High density lipoprotein (HDL) - Triglycerides - Ratio of total/LDL cholesterol 	

Pharmacokinetics: – Somavaratan plasma concentration	Pharmacodynamics: – IGF-I – IGFBP-3
Immunogenicity: – Anti-drug antibodies (ADA) detection and characterization	

5.5.2 Sample Collection, Storage, and Shipping

The safety, PK/PD and immunogenicity assessments require blood samples to be collected during the study. The total annual blood volume required to be collected over the course of the study will differ depending on the duration of dose titration. Estimated annual maximum blood sample volumes (based on 4 months of titration) are detailed in Table 4 below:

Table 4 Maximum Annual Blood Volumes Required

Sample Type	Blood Volume (mL) per Sample	Collection Schedule ¹							Total Number of Time-points	Total per Subject (mL)
		Screen	D1	M1,2	M3	M6	M9	M12		
Hematology (CBC)	2.0	X	X		X	X	X	X	6	12.0
Chemistry, lipid, thyroid panel	10.5	X	X		X	X	X	X	6	63.0
Glucose metabolism	9.5	X	X		X	X	X	X	6	57.0
PK ²	2.0		X	X	X	X	X	X	18	36.0
PD ²	7.0	X	X	X	X	X	X	X	19	133.0
Immunogenicity	3.5		X	X	X	X	X	X	6	21.0
ACTH stim test	8.0	X							1	8
Pregnancy (hCG)	3.5	X							1	3.5
Total Maximum Annual Blood Volume Collection									333.5	

- 1: After the first year all blood sample collections will occur every 6 months.
- 2: PK/PD samples (IGF-I and IGFBP-3) are to be collected at pre-dose and 7 days after dosing (Day 8 ± 1 day) of each month until maintenance dosing is achieved and then quarterly thereafter (maximum volume calculations assume 4 months of titration).

5.6 Dispensing Study Drug

5.6.1 During Titration Period

All Day 1 somavaratan doses during titration will be prepared and administered in clinic by a qualified health care professional. Day 16 somavaratan doses may be administered in clinic or at home by trained subjects/caregivers, or a health care professional

5.6.2 *During Maintenance Period*

All somavaratan doses be administered in clinic or at home by trained subjects/caregivers, or a health care professional.

5.6.3 *Dispensation Records*

The study Investigator must maintain adequate records of receipt, dispensing and return/destruction of all DP. Shipments of DP will be reviewed upon receipt and contents verified with notification sent to the Sponsor or its designee. Exact records of dispensation and return from investigational pharmacy must be maintained including the following information:

- Identification of study subject by study number and initials
- Date of dispensation
- Quantity of DP vials and/or autoinjector devices dispensed (primary container)
- Signature and date of dispensing pharmacist or other trained/authorized personnel
- Date used/unused DP are returned to site

An Investigational Product Accountability Log will be provided by the Sponsor or its designee. Institution-required logs/documents may be used provided they contain the study-required elements and are approved by the Sponsor or its designee.

All dispensed DP vials and/or autoinjector devices (used, partially used or unused) will be returned to the site for drug accountability reconciliation. Other study supplies used at home may be discarded by the subjects/caregivers. Safety containers will be provided to subjects/caregivers for safe disposal of used needles and syringes and/or return of used autoinjector devices. After verification by the Study Monitor, the unused somavaratan DP and other study supplies used on site may be destroyed or returned to the Sponsor's designated investigational product storage facility. Details for destruction and/or return are provided in the Pharmacy Manual.

5.7 *Adverse Event Assessments*

An AE is any untoward medical occurrence in a clinical investigation subject administered a pharmaceutical product which does not necessarily have a causal relationship with this treatment. An AE can therefore be any unfavorable and unintended sign (including an abnormal laboratory finding, for example), symptom, or disease temporally associated with the use of a medicinal product, whether or not related to the medicinal product.

AEs may include increases in intensity or frequency of conditions or diseases that were pre-existing prior to study participation. Examples might include a subject in whom routine headaches become more severe or begin to occur more frequently. Medical or surgical procedures are not in and of themselves considered AEs, but if a condition or disease led to the

procedure, the condition or disease would be considered an AE unless it was present prior to entering the study and did not worsen after entering the study.

AEs may include sequelae of overdose, drug abuse/misuse reports, lack of efficacy, or occupational exposure. In the absence of associated sequelae, these events should be reported as Special Situations and not AEs. Situations in which an untoward medical occurrence has not occurred (e.g., hospitalization for elective surgery or social reasons) are also not considered AEs.

AEs will be reported using the terms in the CTCAE V.4.0 grading scale. A copy will be supplied in the Study Manual, and it can be found online at <http://evs.nci.nih.gov/ftp1/CTCAE> and <http://safetyprofiler-ctep.nci.nih.gov/ctc/ctc.aspx>.

Subjects entering the study with ongoing Baseline medical conditions should have their signs/symptoms graded according to CTCAE V.4.0 criteria. Increases in CTCAE V.4.0 grading from Baseline conditions (e.g., Grade 1 to Grade 2) will be considered adverse events.

A non-serious AE is any AE that does not meet the definition of a serious adverse event below.

5.7.1 Performing Adverse Events Assessments

AEs will be collected at each visit to the health care facility.

5.7.2 Timing

Recording of AEs should begin after informed consent is obtained. AEs occurring after study drug administration are treatment emergent AEs.

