8 PLANNED STATISTICAL METHODS

8.1 General Considerations

This section presents a brief summary of the planned statistical analyses. A statistical analysis plan that describes the details of the analyses to be conducted will be finalized prior to database lock and un-blinding.

All summaries will be presented by cohort.

Summary statistics will be provided for the variables described below as follows. For continuous variables, these statistics will include the number of subjects, mean, standard deviation (SD), median, minimum, and maximum. For categorical variables, these statistics will include the number and percentage of subjects in each category.

The last observation obtained prior to the first dose in the current study will be used as the Baseline value for calculating change from Baseline.

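### The treatment-emergent AE definition has no worsening rule and the AE Baseline is scheduled at Screening, so symptoms that change between Screening and Day 1 may be missed or classified inconsistently

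*Combined protocol and SAP*

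**What the plan says.** - **Start of recording (Section 5.7.2).** "Recording of AEs should begin after informed consent is obtained". Pre-dose AEs will therefore exist in the data.
- **Treatment-emergent rule (Section 5.7.2).** "AEs occurring after study drug administration are treatment emergent AEs". No sentence deals with worsening or recurrence, and no end of the window is given.
- **When Baseline is taken (Section 5.2).** "Baseline signs and symptoms will be obtained as part of enrollment activities during the Screening visit". Section 6.1.1 item 3 has these graded by CTCAE at Screening, and the schedule in Appendix 1 marks that row at Screening only.
- **Worsening as an AE (Section 5.7).** "Increases in CTCAE V.4.0 grading from Baseline conditions (e.g., Grade 1 to Grade 2) will be considered adverse events". The same section adds: "AEs may include increases in intensity or frequency of conditions or diseases that were pre-existing prior to study participation".
- **Second grading (Section 6.1.2 item 1).** Ongoing observations are graded by CTCAE again on Day 1, before dosing.
- **Statistical Baseline (Section 8.1).** "The last observation obtained prior to the first dose in the current study will be used as the Baseline value". The sentence goes on to limit this to the calculation of change from Baseline.
- **Washout (Section 5).** "Minimum of 14 day washout period for subjects currently receiving daily rhGH treatment". It is listed under the Screening period of up to 30 days.

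**The concern.** The sections use two possible reference points for a symptom grade, Screening and Day 1 before dosing, and do not say which one decides whether an on-drug symptom is an AE. For most subjects the two will agree. They can differ for new subjects coming from daily rhGH, because growth hormone is withdrawn between them. Headache, arthralgia and generalized edema are among the events that Section 5.7.5 lists as already reported as related to somavaratan in adults, so a symptom that eases in washout and returns on somavaratan is plausible.

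Safety is the primary objective, and Section 8.5 names TEAE summaries first among the AE outputs. The study is descriptive, so the definition itself determines the reported incidence. A site that sees a returning symptom no worse than its Screening grade could reasonably record nothing, and what is not recorded cannot be recovered by later programming.

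**Working it through.** The plan states no figure for this point, so there is none to reproduce. The check is to take every possible grade path and see which reference point recognizes it.

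**Set-up.** Let S be the grade at Screening, D the grade on Day 1 before dosing, and T the grade on drug, each from 0 (absent) to 3. Keep the paths where the subject is worse on drug than just before it, T > D. There are 6 pairs (D, T) with T > D and 4 values of S, so 6 × 4 = 24 paths. A path counts as an increase from Baseline if T > S (Screening as reference) or if T > D (Day 1 as reference).

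| Path | Possible | Counted, Screening reference | Counted, Day 1 reference |
|---|---|---|---|
| Absent at Screening and Day 1, appears on drug | 3 | 3 | 3 |
| Same non-zero grade at Screening and Day 1, worse on drug | 3 | 3 | 3 |
| Absent at Screening, present on Day 1, worse on drug | 3 | 3 | 3 |
| Present at Screening, absent on Day 1, returns on drug | 9 | 3 | 9 |
| Present at both but at different grades, above Day 1 on drug | 6 | 2 | 6 |
| Total | 24 | 14 | 24 |

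These are counts of paths, not expected event rates.

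**Reading the table.**
1. A stable condition that worsens on drug is counted under either reference. Section 5.7 already makes that increase an AE, and it occurs after dosing.
2. An event that begins between consent and Day 1 and worsens on drug exceeds its Screening grade in 3 of 3 paths. The Screening reference does not lose it. It fails to be treatment emergent only if it stays a single record with a pre-dose start date and the flag is set from that date. The documents specify neither, so this is an ambiguity.
3. The clear difference is the returning symptom: 3 of 9 paths against 9 of 9. The 6 at risk are returns at or below the Screening grade. A further 4 of 6 paths are at risk where the symptom eases without clearing. Together 6 + 4 = 10 = 24 − 14.

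**Who can be affected through washout.** Section 3.1 gives about 40 new subjects and a maximum of 250: 40/250 = 16%. Only those on daily rhGH have a washout, and the split is not stated. If 25%, 50% or 100% of the 40 are switchers (assumed), that is 10, 20 or 40 subjects, or 10/250 = 4%, 20/250 = 8% or 40/250 = 16% of maximum enrolment. The proportion with a symptom that eases and returns is not given, so the number of events missed cannot be computed.

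**The case against.** The strongest reply is that the plan leaves a detail open and does not prescribe a wrong comparison. A reader might infer that on-drug grades are compared with Screening instead of Day 1. No section says so: Section 5.2 and Appendix 1 fix when Baseline symptoms are collected, Section 6.1.2 grades them again before dosing, and Section 8.1 favors the last pre-dose value. This stands, and it is why the point is about ambiguity. It does not close the gap, because Section 8.1 speaks only of change from Baseline and no section makes the Day 1 grade the AE reference.

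A returning symptom can also be read as a new untoward occurrence under the general definition in Section 5.7, or as an increase in frequency. That is fair, and it means some sites would record it. Others, following the grade-increase rule, might not.

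It is also not established that symptoms are graded before washout. Section 4.5 describes subjects who may be on daily rhGH at Screening, but Section 5 puts washout inside the Screening period, and inclusion criterion 3 needs an IGF-I SDS of 0 or below at Screening, which could push some assessments later. The order may therefore vary between subjects.

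Finally, Sections 8.1 and 9.10 leave details to a separate SAP, which may settle the TEAE flag, and the synopsis plans summaries of all AEs. Both answers help for events that were recorded. Neither helps for a recurrence that the site never entered.

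**Conclusion.** The point holds as a gap in definition and collection. A symptom present at Screening, absent on Day 1 and returning on somavaratan at the same or a lower grade may go unrecorded. An event starting between consent and Day 1 and worsening on drug may be flagged differently from one record to the next. The first depends on Screening grading preceding washout and on the site taking Screening as its reference; the second depends on how worsening is entered and flagged.

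A reader might go further and infer that treatment-emergent status rests on start date alone and that such events drop out of the TEAE tables. The documents do not support that: the rule speaks of events occurring, not starting, after study drug, and Section 5.7 makes worsening an AE in its own right.

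A reader might also put a size on it. Assuming 10 to 30 switchers (25% to 75% of 40) and 10% to 30% of them affected gives 10 × 0.10 = 1 to 30 × 0.30 = 9 subjects, or 1/40 = 2.5% to 9/40 = 22.5% of new subjects. Both shares are assumptions. The calculation also needs every such event to be lost and no affected subject to have another TEAE, so the effect on overall TEAE incidence could be zero. What the documents support is a ceiling on the population exposed through washout, about 16% of maximum enrolment, and no estimate of the effect.

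**What to change.** - **Section 5.7.2:** define a TEAE as an AE with onset after the first 15VR8 dose, or one present before that dose whose CTCAE grade rises above its Day 1 pre-dose grade, through the follow-up contact 60 days after the final dose (Section 6.1.8).
- **Sections 5.2 and 5.7:** make the Day 1 pre-dose grade the AE Baseline, so that a symptom absent on Day 1 that appears after dosing is recorded as a new AE whatever its Screening grade.
- **SAP:** carry the same rule into the TEAE flag.

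The Day 1 grade is already collected under Section 6.1.2 item 1, so no visit or procedure is added, and symptoms then share the last-pre-dose principle of Section 8.1. The cost is a few sentences of text and matching site instructions. The reported TEAE count may rise slightly.
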